### Dose Modifications for Hematologic Toxicity

#### First Day of Cycle 2 and Beyond

In order to start Cycle 2 and subsequent cycles as scheduled, on Day 1 of the cycle, patients must have an ANC  $\geq 1.5 \times 10^9/L$ , platelet count  $\geq 100 \times 10^9/L$ , and nonhematologic drug-related toxicities (except alopecia) must be  $\leq$  Grade 1 or have returned to baseline. The dose adjustments in [Table 8-2](#) are based on the ANC and platelet counts on the first day of treatment for Cycle 2 and each subsequent cycle.

**Table 8-2 Etoposide and Carboplatin Dose Adjustments Based on Lack of Recovery of Absolute Neutrophil or Platelet Counts on the First Day of Cycle 2 and Each Successive Cycle**

Absolute Neutrophil Count <math>1.5 \times 10^9/L</math>	Etoposide	Carboplatin
First episode	No change. Use G-CSF with subsequent cycles. Refer to the American Society of Clinical Oncology (ASCO) guidelines (Smith 2006).	No change. Use G-CSF with subsequent cycles. Refer to ASCO guidelines (Smith 2006).
Second episode	First dose reduction	First dose reduction
Third episode	Second dose reduction	Second dose reduction
Fourth episode	Discontinue drug	Discontinue drug
Platelet Count <math>100 \times 10^9/L</math>	Etoposide	Carboplatin
First episode	First dose reduction	First dose reduction
Second episode	Second dose reduction	Second dose reduction
Third episode	Discontinue drug	Discontinue drug

G-CSF = granulocyte colony-stimulating factor

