**Table 8-4 Etoposide and Carboplatin Dose Adjustment Based on Platelet Nadir**

Platelet Count Nadir	Etoposide	Carboplatin
Grade 4 or ≥ Grade 3 with bleeding		
First episode	First dose reduction	First dose reduction
Second episode	Second dose reduction	Second dose reduction
Third episode	Discontinue drug	Discontinue drug

Colony Stimulating Factors

**Patients will not receive colony stimulating factors (eg, granulocyte colony-stimulating factor [G-CSF]; granulocyte-macrophage colony-stimulating factor [GM-CSF]) or erythropoiesis stimulating agents (ESAs) during Cycle 1 (ie, prior to the actual Cycle 2 Day 1 dosing visit).** Subsequent use will be based on toxicities as outlined above. Please also refer to the ASCO guidelines ([Smith 2006](#)) for neutropenia. For a hemoglobin level < 9.0 g/dL or symptomatic anemia, ESAs may be used per the current prescribing information.

When indicated, as outlined above in [Table 8-2](#) and [Table 8-3](#), either filgrastim or pegfilgrastim may be used per the prescribing information detailed in the package inserts (see [Appendix 3](#)). In the event a patient has a neutropenic event requiring G-CSF in the subsequent cycle, then filgrastim or pegfilgrastim should not be initiated until at least 24 hours after dosing of the next subsequent cycle is complete (ie, no earlier than Day 4 of the next subsequent cycle). Filgrastim or pegfilgrastim should not be used to increase low neutrophil counts mid-cycle or prior to the start of the subsequent cycle.

When indicated, epoetin alfa or darbepoetin alfa may be used to treat patients with anemia per the prescribing information detailed in the package inserts (see [Appendix 4](#)).

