### **13.1. Sample Size and Power**

The sample size for this study is determined by clinical rather than statistical considerations. Up to 40 patients (open-label, dose-finding cohort[s] and an open-label, expansion cohort) will be enrolled in Part 1 of the study and 70 patients will be enrolled in Part 2 of the study (randomized). With 35 patients, the precision for point estimates in each arm is as follows: the 95% confidence interval (CI) width for binary endpoints based on Wilson score intervals are at most the observed proportion  $\pm 0.157$ . The 95% CI width for continuous endpoints using the t-distribution are the observed mean  $\pm 0.344$ \*standard deviation of the endpoint.

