2.3. Number of Patients

Overall, up to 110 patients will be enrolled in the study. The sample size for this study is determined by clinical rather than statistical considerations.

In Part 1, approximately 40 patients will be enrolled, assuming up to 3 cohorts. Cohorts will consist of 6 patients each in the Phase 1b dose-finding portion of Part 1 and up to 18 patients in the Phase 2a expansion portion of Part 1 at the selected dose to be used in Part 2. Additional patients may be enrolled in the Phase 1b dose-finding portion of Part 1 if more than 1 cohort is enrolled. In Part 2, 70 patients will be randomly assigned (1:1 ratio) to 1 of 2 groups: G1T28 administered IV with E/P therapy (Group 1) or placebo administered IV with E/P therapy (Group 2). With 35 patients, the precision for point estimates in each arm is as follows: the 95% confidence interval (CI) width for binary endpoints based on Wilson score intervals are at most the observed proportion ± 0.157 . The 95% CI width for continuous endpoints using the t-distribution are the observed mean ± 0.344 *standard deviation of the endpoint.

The study will be conducted at up to 80 centers in North America and Europe.

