5.1.1.8. Duration of Grade 4 Neutropenia

Grade 4 neutropenia is defined as the lab value of ANC \geq Grade 4 event CTCAE toxicity grade criteria (i.e. ANC value is $< 0.5 \times 10^9/L$). For the treatment period, the total number of Grade 4 neutropenia events is the number of cycles where at least one ANC value is $< 0.5 \times 10^9/L$. For example, if Cycle 2 has two ANC values that are both $< 0.5 \times 10^9/L$, this only counts as one event. If a patient did not have any ANC \geq Grade 4 events, the value of 0 will be assigned to that patient. Unscheduled data and the actual assessment date (rather than visit date) will be included in the derivation.

Within each cycle, the duration (days) of each reported Grade 4 neutropenia event is defined as the number of days from the date of first ANC value of $< 0.5 \times 10^9/L$ observed between start of cycle and end of cycle, to the date of first ANC value $\geq 0.5 \times 10^9/L$ that meets the following criteria: (1) occurs after the ANC value of $< 0.5 \times 10^9/L$ and (2) no other ANC values $< 0.5 \times 10^9/L$ occur between this day and end of cycle. The following censoring rules will be applied in the calculation:

- (i) For a cycle where the Grade 4 neutropenia event does not resolve by end of the cycle, the duration will be assigned as above except the end date will be the end of cycle.
- (ii) For a cycle where the patient dies, withdraws consent, or is lost to follow-up during the Grade 4 neutropenia event, the duration will be assigned as above except the end date will be the date of the last ANC assessment prior to the end of cycle.

For the treatment period, the overall duration (days) of Grade 4 neutropenia events is the median value among the duration (days) of Grade 4 neutropenia events from all cycles. The following data handling conventions will apply:

- For those patients where all event duration values are derived from cycles with censored data, the median value for that patient will be the median censored value. It will be a considered a censored value;
- For those patients where a subset of event duration values are derived from cycles with censored data, the median value for that patient will be estimated using the KM method. It will be considered as an observed value (i.e. no censored value);

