6.2.7. Efficacy Analyses

All the efficacy variables will be summarized using descriptive statistics by cycle or visit, with the supportive data provided in patient listings. Part 1 will be summarized using only descriptive statistics. For Part 2, in addition to the descriptive summary, the between treatment comparison (trilaciclib vs placebo), if applicable, will be performed only for those prospectively-defined endpoints outlined in [Section 5.1.1](#). For these comparisons, all statistical tests will be conducted at a two-sided significance level of 20% unless otherwise specified. Where appropriate, model-based point estimates, together with their two-sided 80% CIs will be presented along with the two-sided p-value for the test. Graphical presentation of efficacy results will be appropriately performed as needed.

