the two-sided p-value will be obtained from the stratified Kaplan-Meier method to account for the ECOG status (0-1 vs 2) as the stratification factor. The hazard ratio (HR) between the two treatments (trilaciclib vs placebo), together with its 80% CIs will be calculated from a Cox proportional hazard model in which treatment and baseline ECOG status (0-1 vs 2) will be included as fixed effects. For the time (days) to first occurrence of a MAHE event, a graphical display of cumulative incidence will be presented.

For the endpoints specified in [Section 5.1.1.10](#), in addition to descriptive statistics summary, appropriate graphical display will be provided to help viewing the trend of change over time. Moreover, each of the ANC change over time (i.e. observed value at windowed visit, cycle NADIR, and ANC at each scheduled Day 1 of a cycle) specified above will be done using three distinct data sets to evaluate the confounding effect of GCSF administration: all patients or cycles regardless of GCSF administration; inclusion of only those patients or cycles who had concurrent GCSF administration; and inclusion of only those patients or cycles who did NOT have concurrent GCSF administration. The “with” and “without” GCSF analyses are subsets of the total patient or cycles.

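### The with/without-G-CSF ANC sets cannot evaluate confounding, and the SAP plans no between-arm Cycle 1 neutropenia estimate although Cycle 1 is growth-factor-free by protocol

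*SAP*

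**What the plan says.** - **When G-CSF is given.** For a first Day 1 ANC below 1.5 x 10^9/L, Protocol Table 8-2 reads "No change. Use G-CSF with subsequent cycles". Table 8-3 has the same instruction after a first episode of Grade 4 neutropenia lasting 7 days or more, or of Grade 3/4 neutropenia with fever.
- **When it is barred.** Protocol 8.4.4.2, under Colony Stimulating Factors, states "Patients will not receive colony stimulating factors" during Cycle 1, meaning before the actual Cycle 2 Day 1 dosing visit. Section 8.6 repeats this. Section 8.4.4.2 also rules out G-CSF to raise counts in mid-cycle.
- **ANC summaries.** In SAP 6.2.7.1 the windowed ANC values, the cycle nadir and the scheduled Day 1 ANC "will be done using three distinct data sets to evaluate the confounding effect of GCSF administration". The sets are all patients or cycles, those with concurrent G-CSF, and those without. The methods named are descriptive statistics and graphs.
- **Neutropenia duration.** In SAP 5.1.1.8 a patient's overall duration "is the median value among the duration (days) of Grade 4 neutropenia events from all cycles". If a median cannot be derived (the example is two or fewer values), the longest duration is used. SAP 5.1.1.9 does the same for Grade 3/4. SAP 6.2.7.1 attaches a p-value and a hazard ratio to both. Neither definition mentions G-CSF.
- **Testing.** SAP 6.2.7 says that "all statistical tests will be conducted at a two-sided significance level of 20% unless otherwise specified", with 80% CIs. It also plans descriptive summaries of efficacy variables by cycle or visit.
- **What was removed.** Protocol 13.4.2.1 planned an ANCOVA at each cycle, including on nadir, with LS mean differences and 95% CIs. SAP Section 7 lists these models among the analyses removed.

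**The concern.** G-CSF from Cycle 2 onward is a response to the neutrophil count, which is also the outcome. If trilaciclib protects neutrophils, more placebo patients will meet a trigger. Two problems follow.

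First, splitting the ANC data by G-CSF use compares groups that are no longer randomized. The placebo cycles without G-CSF come from patients who have not met a trigger, and the trilaciclib cycles with G-CSF come from patients who met one despite treatment. Neither contrast isolates what G-CSF does to the comparison.

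Second, the tested durations combine the drug's effect with that of differential rescue. The study's stated goal is to evaluate the effect of G1T28 on chemotherapy-induced myelosuppression. A reader will therefore want at least one neutropenia contrast that is both randomized and free of rescue. Cycle 1 can supply it, but the SAP specifies no between-arm Cycle 1 estimate.

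**Working it through.** **1. The plan's own figures.** "In Part 2, 70 patients will be randomly assigned (1:1 ratio) to 1 of 2 groups", so 35 per arm. Protocol 13.1 says "With 35 patients, the precision for point estimates in each arm is as follows" and gives 0.157 (Wilson) and 0.344 x SD.
- Wilson maximum half-width: z / (2√(n + z²)) = 1.96 / (2√(35 + 3.84)) = 0.157.
- t half-width: t(0.975, 34) / √35 = 2.032 / 5.916 = 0.344.

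Both reproduce. They are per-arm precisions. The documents give no duration, SD or G-CSF effect for any neutropenia endpoint, so everything from step 2 on uses constructed or assumed values.

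**2. The patient median by hand (Grade 4 days in successive cycles).** Trilaciclib is 4, 4, 4 unless stated.
- G-CSF shortens later episodes: placebo 8, 4, 4. The medians are 4 and 4, a difference of 0 against 4 days in Cycle 1.
- Two episodes each: placebo 8, 4 and trilaciclib 4, 4. The longest-duration rule gives 8 and 4, the full 4 days.
- G-CSF prevents later episodes: placebo 8, 0, 0. With event cycles only, the scores are 8 and 4. With event-free cycles counted as 0, they are 0 and 4, which reverses the order.

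The result depends on what an event-free cycle contributes. SAP 5.1.1.8 speaks of event durations, but its only value of 0 is for a patient with no events and follows a sentence about event counts.

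**3. Simulated durations.** Assumptions:
- Six cycles, with 8% of patients stopping after each.
- Log nadir ANC centred on log 0.6, with between- and within-patient SD of 0.6 each.
- Grade 4 below 0.5, with duration 2 + 6 x (log 0.5 − log nadir) days, held to 1–18 and rounded.
- G-CSF from the next cycle after 7 or more Grade 4 days, febrile neutropenia (15% of Grade 4 cycles) or a low Day 1 ANC (likelier with a lower nadir).
- Effects on log nadir: trilaciclib 0.60 in every cycle, or 0.30 rising by 0.15 per cycle; G-CSF 0, 0.7 (moderate) or 1.2 (strong).

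Reading A counts event-free cycles as 0. Reading B uses event cycles only, with the longest taken when there are two or fewer. Entries are the mean difference in days (trilaciclib minus placebo; 40,000 per arm). In brackets is the share of 600 trials of 35 per arm rejecting at two-sided 0.20, by an unstratified log-rank test without censoring.

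| Scenario | Cycle 1 | A | B |
|---|---|---|---|
| Constant effect, G-CSF inert | −1.52 (0.82) | −1.45 (0.91) | −1.95 (0.88) |
| Constant, moderate G-CSF | −1.50 (0.81) | −0.73 (0.77) | −1.81 (0.86) |
| Constant, strong G-CSF | −1.51 (0.81) | −0.44 (0.60) | −1.88 (0.88) |
| Growing, moderate G-CSF* | −0.89 (0.50) | −1.25 (0.89) | −1.70 (0.75) |
| Growing, strong G-CSF* | −0.89 (0.46) | −0.56 (0.64) | −1.61 (0.67) |
| No effect, strong G-CSF* | 0.02 (0.24) | 0.00 (0.24) | 0.00 (0.20) |

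*Log nadir also falls by 0.15 (moderate) or 0.10 (strong) per cycle.

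Constant effect, as a share of Cycle 1: A 0.73/1.50 = 49% and 0.44/1.51 = 29%; B 1.81/1.50 = 1.21 and 1.88/1.51 = 1.25. Against the same reading with inert G-CSF: A 0.73/1.45 = 50% and 0.44/1.45 = 30%; B 1.81/1.95 = 93% and 1.88/1.95 = 96%.

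**4. Simulated ANC sets (difference in log nadir, true effect 0.60 in every cycle).** G-CSF was ever used by 59% to 60% of placebo and 39% of trilaciclib patients.

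| G-CSF | Cycle 1 | All cycles | With | Without | Without, Cycles 2–6 |
|---|---|---|---|---|---|
| Inert | 0.60 | 0.61 | 0.52 | 0.54 | 0.49 |
| Strong | 0.59 | 0.40 | 0.52 | 0.53 | 0.47 |

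With inert G-CSF there is nothing to confound, yet both subsets fall short of 0.60. That shortfall is selection alone. When G-CSF becomes strong the subset contrasts barely move, while the all-cycle contrast drops by a third.

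**The case against.** The strongest reply is that the all-cycle analysis is a deliberate choice. SAP Section 4 expects the benefit to be clearer after repeated chemotherapy, and pooling regardless of G-CSF answers a legitimate question about the regimen as used. This stands. It also limits Cycle 1: in both growing-effect scenarios the Cycle 1 test rejected less often (0.46 against 0.64 and 0.67 with strong G-CSF).

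Second, the G-CSF subsets are confined to descriptive ANC summaries, sit beside the all-patients set and never touch the durations. In Cycle 1 the all and without sets coincide, deviations aside, and by-cycle summaries will show ANC by arm. A reader might infer that the subsets replace the randomized comparison or that Cycle 1 is ignored. The documents support neither. What is missing is a prespecified between-arm Cycle 1 estimate with an interval.

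Third, differential rescue is itself reported: G-CSF use is a tested endpoint. Time to first MAHE is also tested, and its components (dose delay due to ANC, Grade 4 neutropenia beyond 5 days, febrile neutropenia) would normally occur before G-CSF given under the tables. This stands too, but MAHE also counts transfusions, platelet-related delays and treatment-related deaths, so it is not a neutropenia estimate.

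Fourth, the study is small, and "The sample size for this study is determined by clinical rather than statistical considerations". That is a reason to add few contrasts.

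**Conclusion.** The point holds in a limited form. The with/without-G-CSF sets select on a consequence of outcome and treatment, so the stated purpose of evaluating confounding is wrong whatever the numbers. The shortfall was modest in the simulated constant-effect case (0.52 to 0.54 against 0.60).

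For the tested durations, a reader might infer that pooling biases the comparison toward no effect. The documents do not support that as a general statement. Pooling changes the question to the effect in the presence of rescue, and it can attenuate the direct effect. With a constant effect, the all-cycle difference was 29% to 49% of the Cycle 1 difference under reading A but 1.2 times it under reading B. With a growing effect and moderate G-CSF it exceeded the Cycle 1 difference even under A. These sizes rest wholly on assumed inputs, and the simulation omits the SAP's censoring and stratification.

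A reader might also take Cycle 1 as guaranteed free of growth factors. It is free by prohibition, so deviations remain possible. Even so, it is the one cycle that is randomized and rescue-free by design, and with the per-cycle ANCOVA removed no between-arm estimate uses it.

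**What to change.** In SAP 6.2.7.1:

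1. Add supplementary between-arm Cycle 1 estimates with CIs (80% under the SAP's convention), in all Part 2 FAS patients as randomized, adjusted for ECOG (0-1 vs 2). Cover duration of Grade 4 neutropenia (0 if none) and ANC nadir; Grade 3/4 duration and any Grade 4 neutropenia are optional. The ANCOVA in Protocol 13.4.2.1 would serve for nadir. Use the lowest Cycle 1 value after dosing, because the SAP Section 5 definition requires a value below cycle baseline and could leave some patients without one. State how a censored Cycle 1 duration enters.
2. Keep the all-cycle duration analyses, labelled as the effect in the presence of rescue G-CSF. State in 5.1.1.8 and 5.1.1.9 whether event-free cycles enter the patient median.
3. Label the with/without-G-CSF sets descriptive and delete the statement that they evaluate confounding.

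The cost is SAP wording and one table from data already derived by cycle. The downside is that Cycle 1 misses cumulative benefit and may have less power if the effect grows over cycles. It should therefore supplement the all-cycle results, not replace them.

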6.2.7.2. Exploratory Efficacy Analyses

For all these exploratory endpoints listed in [Sections 5.1.2.1, 5.1.2.2, 5.1.2.3, and 5.1.2.4](#), the data will only be summarized using descriptive statistics, hence, the general rules outlined in [Section 6.1.1](#) will be followed. Moreover, the supportive data listings will be provided.

6.2.7.3. Exposure Endpoints

The extent of drug exposure and dose modifications is considered as important efficacy endpoints for trilaciclib. The study dosing records and the derived dosing endpoints will be listed.

Duration on treatment and number of cycles will be summarized by treatment. For each study drug, the dosing endpoints described in [Section 5.1.3](#) will be summarized by treatment.

Dose modification will be summarized for each study drug (trilaciclib, etoposide and carboplatin) including the following:

- Number of cycles received;
- Number of missed doses;
- Number of dose reductions;
- Number of dose interruptions;
- Number of patients with missed dose and its reason;
- Number of patients with dose reductions and its reason;
- Number of patients with dose interruption and its reason.

The number of cycles delayed, the number and percentage of patients experiencing a treatment cycle delay and reason for cycle delay will be summarized by treatment. The number of patients discontinuing study drug will also be summarized along with the reason for discontinuation.

6.2.8. Safety Analyses

All safety analyses will be based on the safety analysis set, as defined in [Section 3.1.2](#). Descriptive statistics will be used to summarize the safety outcomes. The continuous safety variables will be summarized at each visit including end of each cycle (the last non-missing assessment during the cycle), end of treatment (the last non-missing assessment during the treatment period), and end of study (the last non-missing assessment during the whole study), if applicable. No inferential analyses of safety data are planned unless otherwise specified.

6.2.8.1. Adverse Events

Number and incidences rates of AEs will be summarized by SOC and/or PT for the following categories of TEAEs: all AEs, SAEs, AEs leading to death, and AEs leading to study drug discontinuation or study withdrawal. Patients with more than one occurrence of the same SOC (PT) will be counted only once within the SOC (PT) categorization.

AEs will also be summarized similarly by CTCAE grade and relationship to study drug (trilaciclib, carboplatin, and etoposide), and the drug related AE summary will be appropriately evaluated by each drug. Should a patient experience more than one occurrence of the same SOC (PT), the patient's worst occurrence (worst grade/most related causality) will be retained in the tabulation.

All AEs, including AEs that started prior to the study medication, will be presented in patient listings. In addition, separate listings of all SAEs, AEs leading to death, drug-related AEs, and AEs leading to study drug discontinuation or study withdrawal will be provided.

For the AEs related to infusion and related to hematologic toxicity, the criteria for identifying them are described in [Section 5.2.1](#). A summary table showing incidence of AEs related to infusion and related to hematologic toxicity will be presented along with its supportive data listing.

6.2.8.2. Laboratory Evaluations

For hematology and clinical chemistry labs the observed values and change from baseline will be summarized for each visit during the treatment period using descriptive statistics.

Toxicities for clinical labs will be characterized according to CTCAE, Version 4.03 ([Table A-1](#) of Appendix when possible), and the frequency and percentage of patients with each CTCAE grade for each visit during the treatment period will be described. Moreover, any occurrence of

grade 3 or grade 4 during the treatment period will be summarized, and shift in grade from baseline to the worst post-baseline value will be summarized. Both the scheduled and unscheduled assessments will be used to identify the worst post-baseline values.

Listings of all laboratory data, its normal reference ranges, and its CTCAE grade (when possible) will be provided.

6.2.8.3. **Vital Signs**

For vital sign parameters Systolic Blood Pressure, Diastolic Blood Pressure, Pulse Rate, Temperature, Weight, the observed values and change from baseline will be summarized using descriptive statistics at each visit during the treatment period.

Additionally, the frequency and percentage of patients with any potentially clinically significant findings (defined in [Table 11](#)) during the treatment period will be presented. A listing of all vital sign data will be provided.

6.2.8.4. **Performance Status**

Descriptive statistics will be presented for ECOG score for the observed values and change from baseline. A listing of ECOG score for all patients will be provided.

6.2.8.5. **Physical Examination**

A listing of physical examination findings for all patients will be provided.

6.2.8.6. **ECG**

Descriptive statistics will be presented for each ECG parameter for the observed values and change from baseline to post baseline. A listing of all ECG data will be provided.

The criteria of potentially clinically significant findings are defined in [Table 13](#). The frequency and percentage of patients with any potentially clinically significant findings during the treatment period will be presented. The supportive data will be provided in patient data listings.

6.2.8.7. **Analyses of Objective Response**

The number and percentage of patients in each category of TPR according to the investigator tumor assessment (CR, PR, SD, PD, or NE) will be presented. Also, the number and percentage of patients in each category of derived BOR (Confirmed CR, Confirmed PR, SD, PD, or NE), ORR, ORR_{UNCONFIRMED} and CBR according to the investigator tumor assessment (Confirmed CR, Confirmed PR, SD, PD, or NE) will be summarized. Detailed information of deriving tumor relevant responses is provided in [Section 5.2.6](#).

Similar analyses will be repeated based on the derived responses according to the RECIST 1.1, and based on the data from BICR. A cross tabulation of BICR BOR versus the derived BOR will be presented, by treatment group.

Estimates of response rate, along with its associated exact 95% two-sided CIs using Clopper-Pearson method will be computed for ORR and CBR within each treatment group.

DOR (investigator, derived, and BICR) will be summarized using the Kaplan-Meier method, displayed graphically when appropriate, and summarized with median, 25% and 75% percentiles, and their 95% CIs.

The binary endpoint (Yes, No) of ORR for the two treatments (trilaciclib and placebo) in Part 2 will be analyzed to compare trilaciclib and placebo using stratum-adjusted method to account for the ECOG status (0-1 vs 2) as the stratification factor. The adjusted proportion difference (trilaciclib vs placebo) and its 80% CIs will be calculated using CMH weight outlined in [Kim et al. 2013](#). The two-sided p-value will be calculated using stratified exact CMH method.

The analyses are based on the response evaluable population and FAS population. The supportive data listings will also be provided.

